5.2.3 Prior and Concomitant Therapy

Any medication or vaccine (including over-the-counter or prescription medicines, vitamins and/or herbal supplements) that the subject is receiving at the time of enrollment, or receives during the study, must be recorded along with the reason for use, date(s) of administration including start and end dates, and dosage information including dose, route and frequency on the appropriate electronic case report form (eCRF).

The AbbVie Emergency Medical Contact should be contacted if there are any questions regarding concomitant or prior therapy(ies).

5.2.3.1 Prior Therapy

Use of a biologic treatment is prohibited other than risankizumab since initiation in Study 1311.5.

Intra-articular corticosteroids are not permitted within the 4 weeks preceding enrollment and throughout the duration of Study M16-244.

5.2.3.2 Concomitant Therapy

Any medication or vaccines (including over-the-counter or prescription medicines, vitamins and/or herbal supplements) that the subject is receiving since Week 24 of Study 1311.5 and during the study, must be recorded along with the reason for use, date(s) of administration including start and end dates, and dosage information including dose, route and frequency on the appropriate eCRF. The following therapies are allowed for concomitant use:

Methotrexate

Any subjects taking MTX (up to 25 mg/week) must be on a stable dose and stable route of administration for at least 4 weeks before enrollment and ideally maintain this dose throughout the study. Reduction in the dose of MTX will be allowed if the subject can no longer tolerate their dose of MTX.

Folic Acid

Subjects on MTX must be taking folic acid supplementation according to local standard of care before enrollment and during the trial to minimize the likelihood of MTX associated toxicity.

Corticosteroids

Treatment with systemic corticosteroids is permitted up to a maximum daily dosage equivalent to prednisone \leq 10 mg and if the dose was stable within the 2 weeks preceding enrolment. The subject should remain on a stable dose throughout the study.

Topical steroids of US class 6 (mild, such as desonide) or US class 7 (least potent, such as hydrocortisone) (see list in Appendix T) will be permitted for use limited to the face, axilla, and/or genitalia. These topical medications should not be used within approximately 24 hours prior to a visit.

Non-Steroidal Anti-Inflammatory Drugs (NSAIDs) or Paracetamol/Acetaminophen

Stable doses of non-steroidal anti-inflammatory drugs (NSAIDs), cyclooxygenase (COX) 2 inhibitors, or Paracetamol/Acetaminophens are allowed throughout the study. Subjects taking NSAIDs should be advised not to take NSAIDs at least 24 hours prior to study visit. Substitution with another NSAID is permitted over the study duration.

Paper diaries will be provided to subjects to record NSAID, COX-2 inhibitors or Paracetamol/Acetaminophen use throughout the Study M16-244.

Vitamin D

If the subject is taking vitamin D supplements, the subject should continue on stable doses throughout the duration of the trial.

Topical therapy

During the course of the study, subjects may continue treatment with medicated shampoos that do not contain corticosteroids, or bland (without beta or alpha hydroxy acids) emollients. Application of these topical therapies for psoriasis, however, should not occur within 24 hours of a study visit.

5.2.3.3 Prohibited Therapy

Use of the following therapies is prohibited from administration of the first dose of study drug in Study 1311.5 throughout the duration of Study M16-244, including any gap between these two studies:

- Investigational products not otherwise described below

- anti-IL-12/23, and anti-IL-17 agents, including ustekinumab and secukinumab
- Cell-depleting therapies including but not limited to anti-CD20 (e.g., rituximab), investigational agents (e.g., CAMPATH, anti-CD4, anti-CD5, anti-CD3, anti-CD19)
- TNF inhibitors
- JAK inhibitor, Apremilast and leflunomide
- Intra-articular injections (including steroids)
- Intramuscular or intravenous corticosteroid treatment
- Topical PsO treatments such as retinoids, Vitamin A analogs, anthralin and steroids except as permitted in Section 5.2.3.2: Concomitant Therapy
- Oral or injectable PsO medications (not biologicals) including retinoids and fumarates, or any other drugs known to possibly benefit PsO
- Photochemotherapy (e.g., PUVA)
- Any drug known to interfere with or to aggravate PsO including but not limited to lithium and interferons
- Phototherapy (e.g., UVA, UVB)
- Low and high potency opioid analgesics (e.g., methadone, hydromorphone, morphine)
- Live or attenuated vaccines

5.2.4 Contraception Recommendations and Pregnancy

Female subjects of childbearing potential must be ready and able to use highly effective methods of birth control per International Conference on Harmonization (ICH) M3 (R2) that result in a low failure rate of less than 1% per year when used consistently and correctly. Or subjects must have only vasectomized sexual partner(s) or be abstinent. The method chosen must be practiced throughout the study including 20 weeks after the last dose of study drug is given.

Women of childbearing potential are defined as having experienced menarche and are:

- not postmenopausal (12 months with no menses without an alternative medical cause)
- not permanently sterilized (e.g., hysterectomy, bilateral oophorectomy or bilateral salpingectomy).

The following is a list of accepted contraception methods.

- combined (estrogen and progestogen containing) hormonal (oral, intravaginal, transdermal) birth control associated with inhibition of ovulation initiated at least 1 month prior to study participation
- progestogen-only hormonal birth control (oral, injectable, implantable) associated with inhibition of ovulation initiated at least 1 month prior to study participation
- intrauterine device (IUD)
- intrauterine hormone-releasing system (IUS).
- Vasectomized sexual partner(s) (the vasectomized partner should have received medical assessment of the surgical success and is the sole sexual partner of the trial participant).
- True abstinence: Refraining from heterosexual intercourse when this is in line with the preferred and usual lifestyle of the subject (periodic abstinence [e.g., calendar, ovulation, symptothermal, post-ovulation methods] and withdrawal are not acceptable).

In addition, both female subjects of childbearing potential and male subjects with female partners of childbearing potential, taking MTX as background medication, must follow the national regulatory guidelines regarding contraception while taking these medications.

See Pregnancy Testing paragraph in Section [5.3.1.1](#) for pregnancy testing instructions.

See [Appendix D](#) for contraception instructions specific to France.

5.3 Efficacy and Safety Assessments/Variables**5.3.1 Efficacy and Safety Measurements Assessed**

Study procedures described are listed in the following section of this protocol and are summarized in tabular format in [Appendix C](#).

5.3.1.1 Study Procedures

Study procedures will be performed at the study visits as specified in [Appendix C](#). Study visits are scheduled at Week 0/Enrollment, Week 4, 12, 24, 36, 48 and 52. Study procedures are discussed in detail in this section, with the exception of drug concentration measurements and antibody measurements (discussed in Section [5.3.2](#)), study drug administration (discussed in Section [5.5.1](#)), and the collection of adverse event (AE) information (discussed in Section [6.1.5](#)). All study data will be recorded in source documents and on the appropriate eCRFs.

Informed Consent

The subject will sign and date a study specific, Independent Ethics Committee (IEC)/Institutional Review Board (IRB) approved, informed consent form before any study specific procedures are performed in order to participate in this study. Details regarding how informed consent will be obtained and documented are provided in Section [9.3](#).

Inclusion/Exclusion Criteria

Subjects will be evaluated to ensure they meet all inclusion criteria and have none of the exclusion criteria at the Week 0 visit.

Medical and Surgical History

Transcribe medical history from Study 1311.5 source documents and record any updates to represent the status of the Medical and Surgical History at the Week 0 visit.

Demographics

The subject's demographic data, including date of birth, gender, race, and ethnicity will be collected.

Physical Examination

A complete or targeted physical examination will be performed at the designated study visits as specified in [Appendix C](#). A complete physical examination will include vital sign assessment and general appearance as well as evaluation of all organ systems.

Targeted physical examination will include vital sign assessment and evaluation of organ systems associated with AE(s) symptoms or laboratory abnormalities. Clinically relevant abnormal findings will be reported as baseline conditions or AEs.

All physical examination findings whether related to an AE or part of a subject's medical history will be recorded on the appropriate eCRF page. For subjects rolling over from Study 1311.5 to the OLE, adverse events ending prior to completion of Study M16-244 ICF will be recorded in preceding Study 1311.5. Abnormalities assessed by the Investigator after the subject has completed the informed consent process of Study M16-244 will be recorded in the eCRFs of Study M16-244.

Vital Signs

Vital signs evaluations will be performed at visits as shown in [Appendix C](#).

This includes temperature, pulse rate, systolic/diastolic blood pressure and respiratory rate. Respiratory rate, pulse rate, and blood pressure will be measured after subjects have been sitting comfortably for at least 5 minutes. Measurement of vital signs should precede blood sampling to avoid the impact of blood sampling on the vital measurements.

12-Lead Electrocardiogram (ECG)

The 12-lead ECGs will be performed as scheduled in [Appendix C](#).

ECGs will be recorded after the subjects have rested for at least 5 minutes in a supine position and will always precede blood sampling. Six limb leads, as specified by Einthoven (I, II and III) and Goldberger (aVR, aVL, aVF), and six pre-cordial leads (V1 – V6), according to Wilson, will be used.

ECGs may be repeated for quality reasons and the repeat used for analysis. Additional ECGs may be collected for safety reasons at the Investigator's discretion. Clinically relevant, abnormal findings will be reported as AEs.

The electronic version of the ECG is regarded as source data. Dated and signed printouts will be stored in the subject's medical file.

Pregnancy Testing

Women of non-childbearing potential (either postmenopausal or permanently surgically sterile as defined in Section [5.2.4](#)) at Baseline in Study M16-244 do not require pregnancy testing.

For women of childbearing potential, as defined in Section [5.2.4](#) a urine pregnancy test will be done locally prior to enrollment at Day 1 (Week 0) and prior to dosing (where applicable) at each subsequent visit. The urine pregnancy test must be negative for the dosing to occur. If a urine pregnancy test is positive or a subject reports being pregnant during the study, the subject must stop dosing, and have blood drawn for a serum pregnancy test that will be analyzed at the central laboratory. If the serum pregnancy test is positive, dosing must be stopped and the subject must follow the discontinuation procedure described in Section [5.4.1](#).

At each visit, the study staff should review the pregnancy avoidance recommendations with each subject of childbearing potential and document this discussion in the subject's source records.

X-Ray Assessments

The modified Total Sharp Score (mTSS) method, including distal interphalangeal joints, will be used to evaluate radiographic evidence of damage.¹ X-rays of hands, wrists and feet will be performed at two time points (Weeks 24 and 48, detailed in [Appendix C](#)). Images will be read centrally for each subject in a random order and without knowledge of time point, or subject identity, or treatment assignment in Study 1311.5. Subjects who prematurely discontinue from study drug will not be required to collect x-rays at each designated time point, unless they received a dose within the 16 weeks prior to the scheduled time point.

See [Appendix D](#) for instructions specific to Germany.

Clinical Laboratory Tests

Subject will be instructed in advance to attend study visits in a fasted state (8 hours no food and only water). If a patient comes in non-fasted where a fasting condition is required, the visit should be performed, the non-fasted condition documented on the laboratory requisition, and the patient reminded about the expected conditions.

Blood samples will be obtained for the laboratory tests listed in [Table 1](#) at the specified time points noted in [Appendix C](#) depending on the subject's status in the study. Blood draws should be performed after all clinical assessments and patient reported outcomes, ECGs, and vital sign determinations are obtained before study drug administration during a visit.

Urine samples will be obtained for urinalysis testing at the specified time points as listed in Table 1 and at the time points noted in [Appendix C](#). The central laboratory will be responsible for performing a macroscopic urinalysis (urine dipstick) on the collected urine specimens. Specified abnormal macroscopic urinalyses will be followed up with a microscopic analysis at the central laboratory.

A certified central laboratory will be utilized to process and provide results for the clinical laboratory tests. All abnormal laboratory tests that are considered clinically significant by the investigator will be followed to a satisfactory resolution. Laboratory abnormalities are considered to be adverse events only if they result in discontinuation from the study, necessitate therapeutic medical intervention, and/or if the Investigator considers them to be an adverse event.

Instructions regarding the collection, processing and shipping of these samples will be provided by the central laboratory chosen for this study.

Table 1. Clinical Laboratory Tests

Category	Test Name
Hematology	Hematocrit (Hct) Hemoglobin (Hb) Red Blood Cell Count/Erythrocytes Reticulocyte Count White Blood Cells/Leukocytes Platelet Count/Thrombocytes
Diff. Automatic	Neutrophils (relative count) Eosinophils (relative count) Basophils (relative count) Monocytes (relative count) Lymphocytes (relative count)
Diff. Manual (if Diff Automatic is abnormal)	Neutrophils, bands (Stabs) Neutrophils, polymorphonuclear (PMN) Eosinophils Basophils Monocytes Lymphocytes
Coagulation	Partial Thromboplastin Time (aPTT) Prothrombin time (INR) Fibrinogen
Enzymes	AST (GOT) ALT (GPT) Alkaline Phosphatase (AP) Creatine Kinase (CK) CK-MB, only if CK is elevated Gamma-Glutamyl Transferase (GGT/γ-GT) Lactic Dehydrogenase (LDH) Amylase Lipase
Electrolytes	Calcium Sodium Potassium Chloride Bicarbonate

Table 1. Clinical Laboratory Tests (Continued)

Category	Test Name
Substrates	Glucose BUN (blood urea nitrogen) Uric acid Creatinine eGFR Bilirubin Total Bilirubin Direct (if total is elevated) Bilirubin Indirect (if total is elevated) Troponin (Reflex, in case of elevated CK) Protein, Total Albumin C-Reactive Protein (CRP) (high sensitivity) Cholesterol, total Triglycerides LDL-Cholesterol HDL-Cholesterol
Urine Pregnancy test (only for women of childbearing potential) tested locally	Human Chorionic Gonadotropin in urine
Serum Pregnancy test (only if urine pregnancy test is positive)	Human Serum Chorionic Gonadotropin
Tuberculosis Screen	TB Skin Test (tested locally) or QuantiFERON®-TB Gold
Urinalysis (dipstick)	Urine Nitrite Urine Protein Urine Glucose Urine Ketone Urobilinogen Urine Bilirubin Urine RBC/Erythrocytes Urine WBC/Leukocytes Urine pH Urine creatinine

Table 1. Clinical Laboratory Tests (Continued)

Category	Test name
Urine-Sediment (microscopic examination, only if urinalysis abnormal)	Urine Sediment Bacteria Urine Cast in Sediment Urine Squamous Epithelial Cells Urine Sed. Crys., Unspecified Urine Sediment RBC/Erythrocytes Urine Sediment WBC/Leucocytes

Clinically relevant abnormal findings will be reported as baseline conditions or AE's. A clinically relevant value may be either in- or outside the reference range. Clinically relevant abnormal laboratory test results must be confirmed and should be repeated until normalization or stabilization or until an alternative explanation has been found.

Abnormal laboratory values will be also graded for intensity by using RCTC Version 2.0 criteria developed by OMERACT.¹¹

See [Appendix D](#) for Japan specific requirements.

Tuberculosis Screening

All subjects will be tested for TB by either the QuantiFERON-TB Gold Test (or equivalent) or a TB Skin Test or equivalent, most commonly the Purified Protein Derivative (PPD) at the Week 24 visit. If premature discontinuation occurs prior to Week 24 visit TB testing should occur at EOS visit as specified in [Appendix C](#).

A TB Skin Test or equivalent should be utilized only when a QuantiFERON[®]-TB Gold Test is not possible for any reason (unless both tests are required per local guidelines).

- QuantiFERON[®]-TB Gold Test will be analyzed by the central laboratory (QuantiFERON test is preferred over TB Skin Test).
- If the QuantiFERON[®]-TB Gold Test is NOT possible (or if both the QuantiFERON[®]-TB Gold Test and the PPD Skin Test are required per local guidelines) the PPD Skin Test will be performed according to standard clinical practice.

- The PPD Skin Test should be read by a licensed healthcare professional between 48 and 72 hours after administration. A subject who does not return within 72 hours will need to be rescheduled for another skin test.
- The reaction will be measured in millimeters (mm) of induration and induration ≥ 5 mm is considered a positive reaction. The absence of induration will be recorded as "0 mm" not "negative."
- If PPD and/or the QuantiFERON[®]-TB Gold test (or IGRA equivalent) is positive, or if there is a repeat indeterminate QuantiFERON[®]-TB Gold test (or IGRA equivalent) upon retesting, subjects may continue in the study if further work up (according to local practice/guidelines) establishes conclusively that the subject has no evidence of active tuberculosis.
- If the subject is diagnosed with active tuberculosis, the subject should not receive any further study drug and follow the premature treatment discontinuation procedure (Early EOT visit) in Section 5.4.1.
- If presence of latent tuberculosis is established, then tuberculosis treatment may be deferred until completion of the trial according to clinical judgment of investigator and local country guidelines and it is also necessary to report it as an adverse event in the source documents and eCRFs.
- If subject is known to have a positive QuantiFERON[®]-TB Gold or PPD test in Study 1311.5 Screening period do not repeat in this study.
- Subjects who have had an ulcerating reaction to the TB Skin Test in the past should not be re-exposed and should not be tested by a PPD skin test.

In the case of a tuberculosis-related adverse event, a supplemental case report form that provides additional information is to be completed by the investigator or designee.

See [Appendix D](#) for TB testing instructions for Japan sites.

Other Safety Parameters

Local Tolerability

Local tolerability at the administration site of the previous subcutaneous injection will be assessed by the investigator according to "swelling," "induration," "heat," "redness,"

"pain," or "other findings" at the specified visits as noted in [Appendix C](#). Any abnormal findings at the injection site during the current visit will be reported as AEs.

Assessments and Patient Reported Outcomes

Clinical and patient reported efficacy endpoints will be assessed over the course of the study at the time points defined in [Appendix C](#). Patient Reported Outcomes (PROs) should be completed by the patient on his/her own in a pre-specified order in a quiet area/room before any other visit assessments or treatments, and, if possible, before any interaction with the investigator or other members of the study team. Details of the following clinical, efficacy and patient reported efficacy assessments are listed in the appendices.

- Tender (68) and Swollen (66) Joint Count
- ACR Response Components
- Dactylitis (LDI)
- Enthesitis (LEI and SPARCC)
- MDA
- DAS28-hsCRP
- EULAR response criteria
- PsARC response
- PASI and sPGA for patients with $\geq 3\%$ BSA of psoriatic plaques at baseline in Study 1311.5 and/or current visit
- mNAPSI
- mTSS

Patient Reported Outcomes

The order of completion should be as follows, applicable for each PRO as specified in [Appendix C](#).

- PtGA

- Patient's Assessment of PsA Pain Intensity (VAS)
- HAQ-DI
- BASDAI – For subjects that presented with inflammatory spondylitis at baseline to Study 1311.5 based on investigator judgment.
- SF-36
- FACIT-F

Study Drug Administration

Refer to Section [5.5.1](#).

Monitoring for Hypersensitivity Reactions

Subjects should be closely monitored for signs and symptoms of hypersensitivity reactions for approximately 2 hours after the first dose administration (baseline visit) and 1 hour after all other dose administrations at study visits. Hypersensitivity reactions should be treated according to medical standards. Pre-medications for further injections might be considered and will be agreed on between investigator and the AbbVie Medical Director.

In the event of a suspected hypersensitivity reaction or other systemic post-dose reaction, a (PK/ADA) blood and urine sample will be collected once within 24 hours of the reaction.

In the event of a suspected systemic hypersensitivity reaction, a supplemental form that provides additional information is be completed by the investigator or designee.

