5.0 Investigational Plan

5.1 Overall Study Design and Plan: Description

This is a 52-week multicenter, single-arm, OLE study to assess safety, tolerability and efficacy of risankizumab in PsA subjects who have completed all doses of study drug and the Week 24 visit of Study 1311.5 (Phase 2 randomized clinical trial in PsA subjects, sponsored by Boehringer Ingelheim).

Subjects who complete all doses of study drug and the Week 24 visit in Study 1311.5, meet all inclusion criteria (Section [5.2.1](#)) and none of the exclusion criteria (Section [5.2.2](#)) have the option to sign the informed consent form and enter the OLE study, receiving risankizumab 150 mg administered every 12 weeks with an additional dose of risankizumab made available at the Week 4 visit for those subjects that have not achieved a protocol defined response (defined as an improvement in tender and swollen joint count of $\geq 20\%$ compared with the baseline in Study 1311.5), provided the investigator believes this may be beneficial to the subject.

If the Study M16-244 Week 0 visit occurs on the same day or in the 4 days following the Study 1311.5 Week 24 visit only selected activities are required as some activities are common to both studies and are not required twice. See Study Activity Table in [Appendix C](#). If the OLE Week 0 visit occurs > 4 days and ≤ 8 weeks after the Study 1311.5 Week 24 visit, all procedures specified in [Appendix C](#) at Week 0 visit are required.

Subjects that enroll in the OLE study are no longer enrolled in Study 1311.5 and will not complete the Week 28 or Week 32 visits in Study 1311.5.

Subjects who are not enrolled in Study M16-244 within 8 weeks of the Study 1311.5 Week 24 visit are not eligible to participate in Study M16-244.

The study is anticipated to enroll up to 180 subjects. Study visits will occur at Week 0/Enrollment, Weeks 4, 12, 24, 36, 48 and 52. A \pm 4 day window is permitted around scheduled study visits after enrollment.

36-Week Treatment Period

[figure not shown]

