Administration of study drug will occur at Week 0, 12, 24 and 36, with an additional dose of rizankizumab made available at the Week 4 visit for those subjects that have not achieved a protocol defined response (defined as an improvement in tender and swollen joint count of \geq 20% compared with the baseline in Study 1311.5), provided the investigator believes this may be beneficial to the subject. Subjects who have not attained a protocol defined response at 2 consecutive visits at Week 12 visit or thereafter, will be discontinued from the OLE study. Other criteria leading to discontinuation of individual subjects in this trial are described in Section [5.4.1](#).

A \pm 4-day window is permitted around scheduled study visits after enrollment. If any visit has to be rescheduled, subsequent visits should follow the original visit date schedule.

Follow-Up Period

Subjects will have follow-up visits at Week 48 and 52 and a Follow-up Phone call 20 weeks after the last dose of study drug. All Follow-up Visit procedures are noted in [Appendix C](#). Subjects who discontinue study drug treatment early will need to attend an early End of Treatment (EOT) visit ideally within 2 weeks after the decision and preferably prior to the administration of any new therapies. An End of Study (EOS) visit 16 weeks after the last dose of study drug and a Follow-up Phone Call 20 weeks after the last dose of study drug is required to determine the status of any ongoing AEs/SAEs or the occurrence of any new AEs/SAEs (see [Appendix C](#) and Section [5.4.1](#)).

A schematic of the study design is shown below in [Figure 2](#).

Figure 2. Study M16-244 Study Design

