D4. Injection site reaction	Local erythema, pain, pruritis, < few days	Erythema, pain, oedema, may include superficial phlebitis, 1 – 2 wks	Prolonged induration, superficial ulceration; includes thrombosis	Major ulceration necrosis requiring surgery
D5. Petechiae (without vasculitis)	Few, transient asymptomatic	Dependent areas, persistent up to 2 wks	Generalised, responsible to treatment; reversible	Prolonged, irreversible, disabling
D6. Photosensitivity	Transient erythema	Painful erythema and oedema requiring topical treatment	Blistering or desquamation, requires systemic corticosteroids	Generalised exfoliation or hospitalisation
D7. Pruritis	Localised, asymptomatic, transient, local treatment	Intense, or generalised, relieved by systematic medication	Intense or generalised; poorly controlled despite treatment	Disabling, irreversible
D8. Rash (not bullous)	Erythema, scattered macular/popular eruption; pruritis transient; TOC or no meds	Diffuse macular/popular eruption or erythema with pruritis; dry desquamation; treatment required	Generalised, moist desquamation, requires systemic corticosteroids; responsive to treatment; reversible	Exfoliative or ulcerating; or requires hospitalisation; or parenteral corticosteroids

D. Dermatologic (Continued)			
D9. Induration/Fibrosis/Thickening (not sclerodermal)	Localized, high density on palpation, reversible, no effect on ADL and not disfiguring	Local areas < 50% body surface, not disfiguring, transient interference with ADL, reversible	Generalized, disfiguring, interferes with ADL, reversible
E. Ear/Nose/Throat			
E1. Hearing loss	Transient, intermittent, no interference with function	Symptomatic, treatment required, reversible	Interferes with function; incomplete response to treatment
E2. Sense of smell	Slightly altered	Markedly altered	Complete loss, reversible
E3. Stomatitis	Asymptomatic	Painful, multiple, can eat	Interferes with nutrition, slowly reversible
E4. Taste disturbance (dysgeusia)	Transiently altered; metallic	Persistently altered; limited effect on eating	Disabling, effect on nutrition
E5. Tinnitus	Intermittent, transient, no interference with function	Requires treatment, reversible	Disabling, or associated with hearing loss
E6. Voice changes (includes hoarseness, loss of voice, laryngitis)	Intermittent hoarseness, able to vocalise	Persistent hoarseness, able to vocalise	Whispered speech, slow return of ability to vocalise

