**Table 7. Analysis Windows for Local Tolerability During the Open Label Treatment Period**

Protocol Specified Visit Week	Lower Bound	Target Day	Upper Bound
0	1	1	1
4	2	29	57
12	58	85	127
24	128	169	211
36	212	253	295

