**11.6 Local Tolerability**

Local tolerability at the administration site of the subcutaneous injection will be assessed by the investigator according to "swelling," "induration," "heat," "redness," "pain," or "other findings" at the specified visits post dosing.

A frequency table for the local tolerability will be provided at each visit by treatment group based on Safety Analysis Set.

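### Protocol and SAP disagree on which injection local tolerability describes; under the protocol wording the table would miss Grade 1–2 reactions and have no window for the Week 36 injection

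*Protocol*

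**What the plan says.** Protocol 5.3.1.1 (Local Tolerability) states: "Local tolerability at the administration site of the previous subcutaneous injection will be assessed by the investigator". Appendix C footnote o repeats this. Both places then add: "Any abnormal findings at the injection site during the current visit will be reported as AEs". Six findings are scored: swelling, induration, heat, redness, pain and other.

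On timing, protocol 5.1 says "Administration of study drug will occur at Week 0, 12, 24 and 36", with an optional further dose at Week 4. It also says "Study visits will occur at Week 0/Enrollment, Weeks 4, 12, 24, 36, 48 and 52", and a ±4 "day window is permitted around scheduled study visits after enrollment". Protocol 5.5.1 keeps subjects on site for about 2 hours after the Week 0 dose and 1 hour after every other dose.

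SAP 11.6 lists the same six findings at the administration site, "at the specified visits post dosing". The word previous is absent. The planned output is a frequency table by visit. SAP Table 7, "Analysis Windows for Local Tolerability During the Open Label Treatment Period", has five rows: Week 0 (Day 1), Week 4 (Days 2–57), Week 12 (58–127), Week 24 (128–211) and Week 36 (212–295).

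Row D4 of protocol Appendix S grades injection-site reactions. Grade 1 lasts less than a few days. Grade 2 reads "Erythema, pain, oedema, may include superficial phlebitis, 1 – 2 wks". Grade 3 includes induration that persists.

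**The concern.** Safety and tolerability is the primary objective, and protocol 5.3.4 names local tolerability as a safety variable. The two documents do not say the same thing about which injection a given row describes.

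If sites follow the protocol sentence, they inspect an injection site weeks after the dose, when a mild or moderate reaction should have resolved by the protocol's own scale. A row of zeros could then mean good tolerability or late inspection, and the table could not tell the two apart. The rows would also carry the wrong label: each would describe an earlier dose, the first would describe a dose from the feeder trial, and the last dose would have no row. SAP Table 14 has no injection-site category among its areas of safety interest, so this table is the only summary dedicated to local reactions.

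**Working it through.** 1. **Table 7 reproduced.** SAP 6.4 splits the interval evenly between adjacent nominal days (29, 85, 169, 253, 337): (29+85)/2 = 57; (85+169)/2 = 127; (169+253)/2 = 211; (253+337)/2 = 295. All four upper bounds match.

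2. **Lag under the protocol wording.** Lag = 7 × (visit week − week of the last earlier dose). The range is ±4 days when that dose was at Week 0, which has no window, and ±8 days when both visits have one.

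| Visit | Injection seen | Lag (days) | Range (days) |
|---|---|---|---|
| Week 4 | Week 0 | 28 | 24–32 |
| Week 12, no optional dose | Week 0 | 84 | 80–88 |
| Week 12, optional dose given | Week 4 | 56 | 48–64 |
| Week 24 | Week 12 | 84 | 76–92 |
| Week 36 | Week 24 | 84 | 76–92 |
| Week 48, if assessed | Week 36 | 84 | 76–92 |

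3. **Against the grading scale.** Grade 2 runs to 14 days at most. The shortest scheduled lag is 24 days, so the margin is 24 − 14 = 10 days. At scheduled visits only Grade 3–4 reactions could be expected to persist.

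4. **Week 36 injection.** The next visit is Week 48, Day 336 ± 4 in protocol Appendix C, so Day 332 at the earliest. That is 332 − 295 = 37 days past the last Table 7 bound. In the copy reviewed, the Appendix C columns cannot be aligned reliably, so whether a Week 48 assessment is scheduled is left open. Even if it is, Table 7 has no row for it.

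5. **Week 0 row.** On Day 1 the only previous injection is one from Study 1311.5. Its date is not in the documents. It may have been placebo, since SAP 11.3 refers to subjects who received placebo in that study.

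6. **The other reading.** If SAP 11.6 means a look at the same visit after dosing, the doses on Days 1, 29 (optional), 85, 169 and 253 each fall inside a Table 7 window, including Week 36. The Week 4 row would then apply only to subjects who took the optional dose, although Appendix C footnote t has all subjects complete the other Week 4 procedures.

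7. **Illustration of size.** The documents give no reaction rate. Assume N = 180, no dropout, no optional dose, a per-injection reaction rate p of 1–10%, and exponentially distributed duration with median m of 3–14 days. Expected positive readings over Weeks 4, 12, 24 and 36 under previous-site scoring are N·p·(0.5^(28/m) + 3·0.5^(84/m)). Under same-visit scoring of four injections they are 4·N·p.
   - p = 0.01, m = 3: 1.8 × 0.00155 = 0.003, against 7.2.
   - p = 0.05, m = 7: 9 × (0.0625 + 3 × 0.0002441) = 0.57, against 36.
   - p = 0.10, m = 14: 18 × (0.25 + 3 × 0.015625) = 5.3, against 72.

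   The same-visit figures are upper limits, because they assume that every reaction is visible at that look.

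**The case against.** The strongest reply is that the table is defined by SAP 11.6, not by the protocol sentence. The SAP drops the word previous, and its five rows are exactly the five possible dosing visits. On that reading every dose has a window. The Week 0 mark for local tolerability in Appendix C also lacks the superscript that lets Study 1311.5 results stand in, which fits an assessment tied to the new injection. Both points stand as far as they go. They make the Study 1311.5 reading of the Week 0 row an inference from the protocol wording rather than a stated rule. They do not settle the matter: sites collect what the protocol asks for, and the SAP phrase also fits a look weeks later.

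The 24-day minimum applies to scheduled visits only. The Week 36 column in Appendix C doubles as the early end-of-treatment visit, which can fall sooner after a dose, and severe injection-site reactions lead to withdrawal under protocol 5.4.1. Protocol 5.5.4 also allows doses as close as 14 days apart in exceptional cases. Some reactions could therefore be seen earlier.

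Adverse events are collected until 20 weeks after study drug stops, graded on the same scale and tabulated by preferred term, severity and relationship. That stands, and it confines the loss to one descriptive table.

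Finally, protocol 3.4 calls local reactions uncommon, and the Appendix S durations are grading criteria, not observed times. Low counts could arise under either timing.

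**Conclusion.** The two documents define one safety variable differently and should be reconciled. Under the protocol wording, scheduled looks come 24 to 92 days after the injection, the table cannot be expected to capture Grade 1–2 reactions, the Week 36 injection (one of four scheduled doses) has no Table 7 window, and one of the five rows would describe a Study 1311.5 injection. These statements rest on reading the word previous literally and on taking the Appendix S durations as typical.

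A reader might go further and infer that the table is empty by construction, that the Week 36 injection can never enter it, or that near-zero counts would be caused by late inspection. The documents do not support this. SAP 11.6 can be read as same-visit scoring, persistent Grade 3–4 reactions would still appear, and no reaction rate is given that would separate late inspection from good tolerability. Nor is the primary safety objective left unanswered, because adverse-event reporting still covers local reactions.

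**What to change.** - State in protocol 5.3.1.1, Appendix C footnote o and SAP 11.6 which injection each assessment describes and when after dosing it is made.
- Record the six findings at the site just injected, at the end of the on-site observation that already follows each dose. Keep the previous-site look as a separate item.
- In SAP 11.6 and Table 7, label each row by the dose assessed, use subjects who received that dose as the denominator, and tabulate post-dose and previous-site findings separately.
- If previous-site findings are tabulated, leave those at Week 0 out of the M16-244 table and add a Week 48 row for the Week 36 injection where that assessment is collected.

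The cost is minor protocol, eCRF and SAP edits and a brief inspection during time that subjects already spend on site. More mild reactions will be recorded. A look at 1 to 2 hours will miss delayed reactions, which will still depend on adverse-event reporting. If data collection is too far advanced to change, the SAP relabelling and the Week 0 and Week 48 rules can still be made on their own.
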